2.2 Secondary Endpoints

Secondary endpoints include differences between *APOL1* positive participants in the intervention and participants in the control group, impact on primary outcomes at 12 months, psycho-behavioral differences of participants between groups and over time, clinician knowledge, attitudes and beliefs at baseline and 12 months, and differences in outcomes between those tested and not tested immediately.

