3.4 Sample Size

The total number of people expected to participate is 2,050. Of the 1800 intervention participants, approximately 250 will test positive. We will thus have approximately 250 high risk, 250 control, and 1550 normal risk participants. The sample size for the study was calculated assuming a 10% improvement in practice guideline-appropriate renal function test ordering in the *APOL1*-positive group (40% estimated) vs. *APOL1*-negative group (30% estimated) to yield 87% power to detect the difference of interest using a two-sided chi-square test. Specifically, this includes measurement of serum creatinine and urine microalbumin. The blood pressure sub-aim, 5mmHg improvement in systolic blood pressure at 3-month follow up in *APOL1*-positive compared with *APOL1*-negative group, can be detected with 95% power.

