Participants will be randomized via the REDCap randomization tool using a stratified randomization scheme by clinical site in a 7:1 ratio of immediate or delayed *APOL1* genetic testing. The Study Coordinator informs the participant of their randomization outcome. A blood (preferred) or saliva sample is collected from participants randomized to immediate testing by the Study Coordinator. Study Coordinators will obtain a genetic sample for control participants at their 12 month visit. Participants are informed that their result will be ready in 2-4 weeks.

The baseline visit will take approximately 1.5 hours to complete. Participants will receive \$40 in gift cards when they have completed their baseline visit.

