8. STATISTICAL ANALYSIS PLAN AND SAMPLE SIZE

8.1 Sample Size Determination

The study will randomize 2050 patients to either immediate or delayed genetic testing in a ratio of 7:1 respectively. We anticipate that of the 1800 patients who will be tested immediately approximately 250 will test positive. For this aim, we hypothesize that APOL1 positive patients will achieve 40% correct utilization of serum creatinine and/or urine albumin tests for “standard renal care” in patients with hypertension, compared to

30% for APOL1 negative patients. With an estimated 250 APOL1 positive and 1550 APOL1 negative we will have 87% power to detect the difference of interest using a two sided chi-square test.

Power calculations for this sub-aim are based on reduction of systolic blood pressure at three months after enrollment. For patients who test APOL1 positive we anticipate a 5 mmHg reduction in systolic blood pressure, compared to no change in patients who test APOL1 negative. Assuming that the standard deviation for differences in blood pressure between baseline and 3 month in both arms is 20 mmHg, a total of 250 patients testing positive and 1550 testing negative provides approximately 95% power to detect a difference of 5 mmHg in SBP between these two groups. If the standard deviation is larger than assumed, say 25 mmHg, power will still exceed 80%. Power is based on a 0.05 level two-tailed t-test of the difference in SBP at 3 months.

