8.4 Analysis of the Secondary Endpoints

Secondary outcomes include differences in SBP and urine testing in an enriched intervention group (*APOL1* positives) vs. controls, and psycho-behavioral patient factors between groups and over time.

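### Section 8 specifies no analysis for immediate versus delayed testing, the as-randomized contrast listed in Section 2.2, and positives versus controls is not aligned on genotype

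*Combined protocol and SAP*

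**What the plan says.** The randomized factor is the timing of testing. Section 8.1: "The study will randomize 2050 patients to either immediate or delayed genetic testing in a ratio of 7:1 respectively". Section 3.1 divides the sample into three groups for comparison: tested positives, tested negatives and the delayed-testing controls. Section 3.4 sizes them: "We will thus have approximately 250 high risk, 250 control, and 1550 normal risk participants".

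Section 2.1 makes positives versus negatives the primary comparison. Section 2.2 then lists several secondary endpoints, among them positives versus controls and "differences in outcomes between those tested and not tested immediately".

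Section 8 treats these contrasts unequally:

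- Section 8.1 gives power for positives versus negatives only.
- Section 8.2 opens with general-purpose tests for comparing groups. It then names mixed models for systolic pressure, and generalized estimating equations for blood pressure control and renal testing. These are for positives versus negatives, and likewise for positives versus controls.
- Section 8.4 reads "Secondary outcomes include differences in SBP and urine testing in an enriched intervention group", set against controls, and adds psycho-behavioral factors. Immediate versus delayed testing is not mentioned.

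On control genotypes, Section 6.2 says: "Study Coordinators will obtain a genetic sample for control participants at their 12 month visit".

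**The concern.** Randomization protects one comparison: everyone assigned to immediate testing against everyone assigned to delayed testing. The primary contrast is between genotypes, which were not randomized. Section 6.6 also plans a different delivery of results for the two genotypes: in person for positives, by telephone for negatives. A difference between positives and negatives could therefore reflect genotype, a response to a positive result, or a response to a reassuring negative one. The delayed arm is what could separate these.

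The contrast with the delayed arm that Section 8 does name sets a group selected to be entirely APOL1-positive against an arm that was not selected on genotype. If positives and negatives would have followed different trends in pressure or test ordering without any result being returned, that difference enters the estimate. Section 8 has no step to align genotype and gives no guidance on interpretation.

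At stake is whether the trial reports what returning the result did, using the randomization it set up, and whether the population, model and time point for that comparison are fixed before the data are seen.

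**Working it through.** **Inputs.** 2050 randomized, planned as 1800 immediate and 250 delayed (Sections 3.4 and 8.1). Section 8.1 on positives: "We anticipate that of the 1800 patients who will be tested immediately approximately 250 will test positive". Renal testing: "we hypothesize that APOL1 positive patients will achieve 40% correct utilization of serum creatinine and/or urine albumin tests", against "30% for APOL1 negative patients". Systolic pressure: 5 mmHg reduction in positives, none in negatives, SD of change 20 mmHg, or 25 as the plan's sensitivity value; two-sided 0.05 (Section 8.1; assumed the same for the chi-square test). Prevalence of two risk alleles: 13% and 15% (Section 1.1). No dropout rate is stated and none is applied.

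**1. The plan's own power, 250 versus 1550.**

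- Testing: pooled rate (100 + 465)/1800 = 0.3139. Null SE = √(0.3139 × 0.6861 × (1/250 + 1/1550)) = 0.0316. Alternative SE = √(0.24/250 + 0.21/1550) = 0.0331. Power = Φ((0.10 − 1.96 × 0.0316)/0.0331) = 87.5% (stated 87%).
- Pressure, SD 20: SE = 20 × √(1/250 + 1/1550) = 1.363. Power = Φ(5/1.363 − 1.96) = 95.6% (stated about 95%). With SD 25: 83.5% (stated above 80%).

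The stated figures reproduce. They cover positives versus negatives only.

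**2. Genotype mix of the control arm.** Of 250 controls, 250 × 0.13 = 32.5 to 250 × 0.15 = 37.5 are expected to be positive, so 85-87% are negative. At the plan's 250/1800 = 13.9%, about 35 are positive and 215 negative.

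**3. As randomized, 1800 versus 250.**

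- Half-width, pressure: 1.96 × 20 × √(1/1800 + 1/250) = 2.6 mmHg (3.3 at SD 25).
- Half-width, testing: 1.96 × √(0.314 × 0.686/1800 + 0.30 × 0.70/250) = 6.1 points.
- Section 8.1 gives no expected values for controls. Assuming that they behave like the planned negatives (30%, no change), the immediate arm would show (250 × 0.40 + 1550 × 0.30)/1800 = 31.4% against 30%, a difference of 1.4 points, and 5 × 250/1800 = 0.69 mmHg.
- Power for those effects: 7.4% (SD 20) or 6.1% (SD 25) for pressure and 6.3% for testing. Counting the far tail gives 8.1% (SD 20) and 7.1%. So about 6-8%.
- Difference detectable with 80% power: about 3.8 mmHg (SD 20) and about 9 points.

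**4. Genotype-matched contrasts, if every control is genotyped.**

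- Positives, 250 versus 35: 1.96 × 20 × √(1/250 + 1/35) = 7.1 mmHg (7.3 to 6.9 for 32.5 to 37.5 controls). At SD 25, 8.8 mmHg. Power for the full 5 mmHg: 28% (SD 20) or 20% (SD 25); for 40% versus 30% testing, 19%.
- Negatives, 1550 versus 215: 1.96 × 20 × √(1/1550 + 1/215) = 2.9 mmHg.

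**5. Positives versus all controls, 250 versus 250, if the full planned differences applied.** Power is 80% (SD 20) or 61% (SD 25) for pressure and 65% for testing. This contrast is more precise than the matched one for positives, but it is not genotype-aligned.

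**The case against.** Several points on the other side are sound.

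- A reader might infer that Section 8 has no analysis at all for the randomized groups, or that the plan never compares them. The documents do not support that. The general tests in Section 8.2 could be applied to any listed contrast, Section 3.1 includes controls among the groups to be compared, and the list in Section 8.4 is worded as non-exhaustive. What stands is that nothing says who is analysed, with which model, or when.
- A reader might infer that the sponsor dropped the contrast because its power is low. No section says so, and Section 2.2 lists it.
- A reader might infer that positives versus controls is biased by any genotype difference. Section 8.2 models change over time and refers to adjustment for confounders, though it names none. Section 6.7 extracts 12 months of records before randomization. Stable level differences are therefore largely removed, leaving differences in trend. Known CKD is excluded (Sections 4.1 and 4.2), which narrows one route to such a difference. The documents give no evidence of one.
- Genotype-matched contrasts are not clean randomized comparisons. The immediate arm is sampled at baseline and controls at 12 months, so a control who leaves early cannot be classified, even with a 3-month pressure reading. The 32 to 38 positive controls are therefore upper figures.
- Power is low for the whole-arm and positive-matched contrasts. That argues for reporting an estimate with its interval and against expecting a decisive test. It does not argue for leaving the analysis open: an interval of about 2.6 mmHg either way still limits how large an overall effect could be.

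**Conclusion.** The point holds in this form: a listed secondary endpoint, the only one in Section 2.2 that clearly preserves randomization, has no specified analysis in Section 8. The named contrast with the delayed arm compares an all-positive group with one expected to be 85-87% negative. The bias this could cause is confined mainly to genotype-related differences in trend, and it is possible but not demonstrated. The primary power calculation is unaffected.

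The as-randomized half-widths rest on the plan's SDs, its testing rates and no dropout. The diluted effects and the 6-8% power rest further on this review's assumption that controls behave like the planned negatives; they would change if a negative result also alters behavior. Even with the change below, the trial would probably not settle whether returning results matters overall, but it would give a prespecified estimate with known precision.

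**What to change.** Amend Section 8.4 as follows.

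(a) Specify immediate versus delayed testing, all participants as randomized, at 3 and 12 months, stratified by site and adjusted for the baseline value. Report an estimate with a 95% confidence interval, and state the expected half-widths (about 2.6 mmHg at SD 20; about 6 points) and the limited power.

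(b) Add two supportive estimates using the 12-month control genotypes: positives-immediate versus positives-delayed (about 7 mmHg either way at SD 20, 9 at SD 25, for at most 32 to 38 control positives) and negatives-immediate versus negatives-delayed (about 2.9 mmHg). State that only controls sampled at 12 months can be classified, report the share with missing genotype by arm, and add a sensitivity analysis restricted to 12-month attenders in both arms. That restriction makes the selection rule the same in both arms, but it still conditions on attendance after randomization.

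(c) State that positives versus all controls is not genotype-aligned, and interpret it accordingly.

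The cost is SAP wording and modest extra analysis of data already planned, with no added visits or enrolment. The drawback is wide intervals, especially for positives.

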3. STUDY DESIGN

3.1 Study Arms & Design

This is a prospective, multicenter, unblinded, randomized clinical trial (RCT) (**Figure 1**). The study was designed to randomize 2050 participants to immediate *APOL1* gene testing and return of results (ROR) (intervention) or delayed *APOL1* gene testing and ROR (control) in a 7:1 ratio. Outcome measures will be compared among three arms of the GUARDD study, the *APOL1*-positive and *APOL1*-negative intervention (immediate *APOL1* genetic testing and return of results) groups, and the control (delayed *APOL1* testing and return of results) group.

[figure not shown]

Figure 1. GUARDD study flowchart.

3.2 Randomization

Eligible participants will be randomized in a 7:1 allocation to Intervention (i.e., immediate *APOL1* gene testing and ROR to participant and provider) and Control arms (delayed *APOL1* gene testing and ROR to participant and provider) to optimize the proportion of participants with immediate *APOL1* genetic testing compared with delayed genetic testing at completion of study. Randomization will be stratified by clinical site with a random block size within site.

3.3 Blinding

GUARDD randomization assignments will not be blinded to any participants, providers or study personnel. To minimize bias in the measurement of the primary outcome, randomization assignments will only be revealed after baseline survey responses and blood pressure readings have been collected. Digital blood pressure devices (such as BpTru portable blood pressure machine (29)) will be used to measure blood pressure, and blood pressure will be measured as the mean of the second and third blood pressure readings for each participant at each study visit.

3.4 Sample Size

The total number of people expected to participate is 2,050. Of the 1800 intervention participants, approximately 250 will test positive. We will thus have approximately 250 high risk, 250 control, and 1550 normal risk participants. The sample size for the study was calculated assuming a 10% improvement in practice guideline-appropriate renal function test ordering in the *APOL1*-positive group (40% estimated) vs. *APOL1*-negative group (30% estimated) to yield 87% power to detect the difference of interest using a two-sided chi-square test. Specifically, this includes measurement of serum creatinine and urine microalbumin. The blood pressure sub-aim, 5mmHg improvement in systolic blood pressure at 3-month follow up in *APOL1*-positive compared with *APOL1*-negative group, can be detected with 95% power.

3.5 CCARP Genomics Subcommittee- Stakeholder Engagement

The CCARP Genomics Subcommittee members comprised of clinicians, researchers and community leaders will be in every stage of the research, including: choosing the study approach, tailoring and shaping the patient education materials, developing and implementing recruitment and retention strategies, deciding what to evaluate with survey questions, and disseminating our findings to the community.

4. STUDY POPULATION

4.1 Inclusion Criteria

- Self-reported African American/Black or having African Ancestry
- English speaking
- Age 18-70 years
- Have diagnosis of hypertension
 - Diagnosis of hypertension is defined by either:
 - ICD9 diagnosis codes (present in encounter diagnosis or in problem list) and/or
 - Taking anti-hypertensive medications or
 - 2 systolic blood pressure readings >140 mm Hg or 2 diastolic readings >90 at least six months apart.
- Received primary care from one of the participating clinical sites ≥ 1 within the past 2 years.
- Do not have diabetes by self report, or defined by:
 - ICD9 diagnosis codes (present in encounter diagnosis or in problem list) or
 - HbA1c ≥ 6.5 at least one time in the last year
- Do not have CKD by self report or defined by either:
 - 1) ICD9 codes OR
 - GFR < 60 ml/min

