Synthesis: Poor adherence with renal care practice guidelines puts participants at risk for kidney failure

Importantly, major goals of practice guidelines for renal care in hypertensive participants remain unmet in clinical practice today: among Medicare participants with hypertension without diabetes, only 1 in 25 receives recommended simple lab tests (creatinine and urine albumin) to evaluate CKD, and less than half of all participants with moderate to advanced stages of CKD in the Kidney Early Evaluation Program (KEEP) are aware that they are affected (23). Among younger participants of African Ancestry CKD awareness is particularly low (23) and progression to kidney failure is typically accelerated resulting in excessive rates of ESRD (13) (18).

Improved CKD awareness and access to primary care or nephrology referral for individuals with or at risk of CKD are considered critical to improve CKD-related outcomes (24, 25). Factors associated with progression of CKD and with increased cardiovascular risk are overlapping to a large extent, including hypertension. There is strong evidence that blockade of the renin-angiotensin system is a blood pressure lowering strategy which is more effective in reducing risk of kidney and cardiovascular disease in the presence of albuminuria, a marker of CKD (26). Thus, in order to improved renal care and reduce risk for kidney failure in this population at excess risk, we urgently need new strategies:

- to improve comprehension of CKD risk and CKD awareness among participants with CKD or at risk for CKD and among their providers, and
- to increase adherence with practice guidelines targeting those risk factors that are modifiable may both reduce cardiovascular disease in people with CKD and reduce progression of CKD to end stage kidney disease.

Synthesis: APOL1 G1 and G2 risk alleles and non-diabetic kidney diseases.

A locus containing the myosin heavy chain 9 (MYH9) gene for non-diabetic kidney disease in African ancestry individuals was initially identified by admixture mapping (27, 28). Recently, three non-synonymous coding

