variants in the neighboring *APOL1* gene defined two allele, termed G1 and G2 with stronger effect on non-diabetic kidney disease than MYH9 variants (19). The authors suggested that G1 and G2 alleles are exceedingly rare in non-African ancestry genomes, but in African ancestry genomes, 22.5% and 14.6% of chromosomes carry the mutually-exclusive G1 and G2 risk alleles because they were selected for by providing protection against Trypanosomiasis (sleeping sickness) in West Africa (19).

APOL1-associated kidney disease risk is best explained using a recessive model, and approximately 13% of African Americans are estimated homozygous for G1 / G2 risk alleles, suggesting that more than 3 million AA are at markedly increased risk for non-diabetic CKD (20). In our IPM Biobank, 15% of more than 5,000 AA participants were found to carry [2] risk alleles, and the odds for hypertensive CKD in this cohort were 2.7. We recently analyzed the effect of APOL risk alleles on severity of hypertension-attributed kidney disease in the African American Study of Kidney Disease and Hypertension (AASK) cohort (Table 1). *APOL1* risk alleles are highly significantly associated with CKD attributed to essential hypertension in non-diabetic AASK participants, and the odds for advanced kidney disease (significant proteinuria or serum creatinine >3 mg/dl) were >4 -fold in carriers of [2] risk alleles compared to [0,1] risk alleles (22). Heterozygous G1 or G2 risk allele status does not appear to increase kidney disease risk.

Table 1. Logistic regression model of the effect of APOL1 risk alleles on clinical phenotype AASK cases and controls

Note: creatinine >2 or >3 mg/dL approximate CKD Stage 3 or higher; ESKD indicates end stage kidney disease, i.e. CKD stage 5; urine PCR (protein creatinine ratio) > 0.22 g/g or > 0.60 g/g correlate approximately with albumin creatinine ratio (ACR) of > 30 mg/g and > 300 mg/g.

In summary, [2] *APOL1* G1 / G2 homozygous risk allele status

- explains practically all of the substantial excess genetic risk for non-diabetic CKD in African ancestry populations,
- is present in 1 out of 7 African American participants genotyped at Mount Sinai,
- is strongly and consistently associated with hypertension-attributable CKD (odds >2.7)
- is strongly and consistently associated with progressive and proteinuric states of hypertension-attributable CKD (odds >4.0) or with hypertensive ESRD (odds 7.3).

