Rationale. CKD awareness among participants and providers, appropriate use of tests for biochemical markers of CKD (creatinine and urinary albumin excretion) to screen for presence of CKD in those at risk, and appropriate use of pharmacological and life style interventions in those at risk for CKD progression are considered critical to improve CKD-related outcomes (ESRD, CVD, and mortality [\(24, 25\)](#)). As summarized in the paragraph “**Synthesis: Poor adherence with renal care practice guidelines puts participants at risk for kidney failure**” at the beginning of the APPROACH section, major goals of practice guidelines for renal care in hypertensive participants remain unmet in clinical practice today. Blacks have higher prevalence of hypertension (41% vs. 28%), younger age of onset, and poorer control of hypertension than Whites [\(17\)](#). Blacks also have, a 2-3x the risk for developing CKD [\(12\)](#), and the adjusted prevalence rate for ESRD is 4.1-fold higher in AA when compared with Whites [\(14-16\)](#). The differences in CKD are most pronounced among those with hypertension. Thus, it is imperative to uncover new strategies to screen and engage AAs with hypertension into programs to improve BP control and participant outcomes.

The Kidney Disease Improvement Global Outcomes (KDIGO) evidence-based practice guidelines advise the appropriate use of tests for biochemical markers of CKD (creatinine and urinary albumin excretion) to screen for presence of CKD in those at risk, and appropriate use of pharmacological and lifestyle interventions in those at risk for CKD progression are considered critical to improve CKD-related outcomes (ESRD, CVD, and mortality [\(24, 25\)](#)). Practice guidelines, including the Joint National Commission 7 (JNC7) guidelines, recommend specific medications (ACE inhibitors and ARBs) as preferred first line agents and more intensive blood pressure goal in participants with hypertensive CKD [\(9-11\)](#).

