4.2 Exclusion Criteria

- Have diabetes measured or by self report
- Have CKD measured or by self report
- Pregnancy at time of enrollment by self report

- Too cognitively impaired to provide informed consent and/or complete the study protocol measured by mini mental status exam
- Institutionalized or too ill to participate (i.e. terminally ill, incarcerated, in psychiatric or nursing home facility) by self report
- Plan to move out of the area within 12 months of enrollment by self report
- Not a patient under the care of a provider for their hypertension at a participating site by self report
- Previously participated in the *APOL1* qualitative pilot study or have previously undergone *APOL1* testing

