6.7 Electronic Health Record Data Extraction

Electronic health data relevant to the study endpoints will be pulled for the period of 12 months prior to randomization and 12 months after randomization for all enrolled participants.

Figure 2. *APOL1* positive BPA Alert

Genomic Medicine – GUARDD Study

POSITIVE RESULT:
This patient has INCREASED RISK for End Stage Kidney Failure according to *APOL1* genetic testing (result: G1/G1)

Evidence suggests that good blood pressure control and renal function testing may forestall kidney failure.

Recent blood pressure readings were:
12/15/2011 3/23/2012 6/1/2013
140/90 130/85 120/80

[Click here for provider information](#)

[Click here for patient materials](#)

Note: These results will be filed under Labs / Genetics.

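### The CKD-free definition has no urine albumin criterion, so patients with recorded albuminuria can be enrolled and may inflate the non-randomized renal-testing contrast by an unknown amount

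*Combined protocol and SAP*

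**What the plan says.** Section 4.1 admits people who "Do not have CKD by self report or defined by either" of ICD9 codes or GFR below 60 ml/min. Section 4.2 excludes those who "Have CKD measured or by self report" and does not say what counts as measured. Section 8.3 lists only CKD as an exclusion.

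The background takes a wider view. Section 1.1 says that renin-angiotensin blockade works better "in the presence of albuminuria, a marker of CKD". The rationale under Sub-Aim 2.2 in section 1.2 names creatinine and urinary albumin excretion together as the biochemical markers. The note to Table 1 equates a urine PCR above 0.22 g/g with an ACR above about 30 mg/g.

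On genotype, section 1.1 reports that in the AASK cohort "the odds for advanced kidney disease (significant proteinuria or serum creatinine >3 mg/dl) were >4 -fold in carriers of [2] risk alleles". It gives odds above 2.7 for hypertension-attributable CKD overall.

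The primary renal endpoint (section 2.1) is clinicians' correct use of urine albumin tests, compared between APOL1 positives and negatives at three months. Section 3.2 randomizes only the timing of testing. EHR data "will be pulled for the period of 12 months prior to randomization" and for 12 months after it (section 6.7).

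**The concern.** Positives and negatives are formed by genotype, so randomization does not balance them. The protocol's own rationale is that this genotype raises the risk of kidney disease. If kidney disease that is already visible in the record stays in the sample, it is linked both to the exposure (genotype) and to the outcome, because an abnormal urine albumin is itself a reason to repeat the test.

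The listed criteria leave that opening. A patient with a recorded ACR of 200 mg/g, a GFR of 85, no CKD code and no awareness meets all of them. Unawareness is plausible: section 1.1 says that fewer than half of screening-program participants with moderate to advanced CKD knew of it.

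At stake is whether more testing among positives can be credited to the returned result. The planned analysis gives no clear protection. The sample size in section 8.1 rests on an unadjusted chi-square test. Section 8.2 mentions adjustment for confounders in the SBP model, without naming them, and lists no covariates for renal testing.

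**Working it through.** **1. The plan's own figure.** Inputs from section 8.1: 40% versus 30%, 250 versus 1550, two-sided chi-square. Alpha is stated only for SBP, so 0.05 is assumed here.

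- Pooled rate = (250×0.40 + 1550×0.30)/1800 = 0.314.
- Null SE = √[0.314×0.686×(1/250 + 1/1550)] = 0.0316.
- Alternative SE = √(0.24/250 + 0.21/1550) = 0.0331.
- Power = Φ[(0.10 − 1.96×0.0316)/0.0331] = 87.5%.

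The stated 87% reproduces. The point does not rest on an arithmetic error.

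**2. Inputs for the bias.**

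- Odds ratio, positives versus negatives: 2.7 or 4, from section 1.1. Applying either value to this population is extrapolation.
- Known albuminuria in negatives (f): not in the documents; assumed.
- Three-month testing: 70% with known albuminuria and 27% otherwise; assumed. At f = 5% the negatives' overall rate is 0.70×0.05 + 0.27×0.95 = 29.2%, close to the plan's 30%.
- Effect of disclosure: set to zero.

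**3. Formulas.** With o = f/(1 − f), prevalence in positives is p = OR×o/(1 + OR×o). Spurious difference = (p − f)×(0.70 − 0.27).

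| f | p, OR 2.7 | p, OR 4 | Spurious difference (points) |
|---|---|---|---|
| 0.4% | 1.1% | 1.6% | 0.3 to 0.5 |
| 0.8% | 2.1% | 3.1% | 0.6 to 1.0 |
| 2% | 5.2% | 7.5% | 1.4 to 2.4 |
| 5% | 12.4% | 17.4% | 3.2 to 5.3 |

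Example for f = 5%, OR 4: o = 0.05/0.95 = 0.0526; p = 0.2105/1.2105 = 0.174; (0.174 − 0.05)×0.43 = 5.3 points.

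**4. Effect on the test.** Holding the negatives at exactly 30%, with 70% testing in known albuminuria and no disclosure effect, the rejection rate of the nominal 5% chi-square test is as follows.

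| f | OR | Difference (points) | Rejection rate |
|---|---|---|---|
| 2% | 2.7 | 1.3 | 7% |
| 2% | 4 | 2.3 | 11% |
| 5% | 2.7 | 3.1 | 17% |
| 5% | 4 | 5.2 | 39% |

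**5. Which f is plausible?** Only recorded albuminuria matters here. Section 1.1 says that 1 in 25 Medicare patients with hypertension and no diabetes receives the recommended tests. If that 4% held here, f could not exceed 4%; with 10% to 20% of tests abnormal (assumed), f = 0.4% to 0.8%. The plan's 30% rate, which section 8.1 defines on creatinine and/or urine albumin, allows more. With 30% tested for urine albumin, f = 2% needs 1 in 15 tests abnormal and f = 5% needs 1 in 6.

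**6. Cost of excluding flagged participants.** At f = 5%, positives fall to 250×(1 − 0.124) = 219 or 250×(1 − 0.174) = 207, and negatives to 1550×0.95 = 1473. The formula in step 1 then gives 83% or 82% power.

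**The case against.** The best answer is that the affected group is narrow and partly handled. Clinicians must know of the albuminuria well enough to monitor it, yet enter no code, while the patient stays unaware. The undefined measured-CKD exclusion in section 4.2 may remove some of these patients. Section 8.2 plans GEE on change in renal testing, and 12 months of earlier EHR data are available, so a stable difference in testing frequency would largely cancel. The 1-in-25 figure points to low prevalence. All of this stands as a reason for caution about size. It does not close the gap: the chi-square test on which the study is powered has no baseline term, and GEE on change does not remove the effect of a recent abnormal value that alters later ordering. The secondary comparison with controls (sections 2.2 and 8.4) does not escape either, because controls are of mixed genotype.

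Three stronger readings are tempting, and the documents do not support them.

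- *Albuminuria is over four times as likely in positives.* The source gives odds, and for significant proteinuria or creatinine above 3 mg/dl in AASK, not for uncoded albuminuria at a GFR of 60 or more in primary care. At f = 5% an odds ratio of 4 is a risk ratio of 17.4/5 = 3.5.
- *The bias could account for most of the planned effect.* With the same testing rates, f = 10% would give 5.6 to 8.9 points, but even with 30% of patients tested it needs one test in three to be abnormal among people with no code, no self-reported CKD and preserved GFR. Nothing in the documents supports that, or the 70% re-testing rate.
- *Both primary endpoints are biased.* Section 1.2 does mention a "more intensive blood pressure goal in participants with hypertensive CKD", but that concerns diagnosed patients, who would often be excluded. The SBP endpoint is a reduction, so treatment tightened before enrollment is already in the baseline reading. No SBP effect can be quantified.

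**Conclusion.** The gap is real and can be read directly from the text: the eligibility sections and the background disagree on whether albuminuria marks CKD, and such patients can be enrolled. The gap opens a route by which positives could be tested more with no effect of disclosure. The direction follows from the protocol's own genotype associations; the size cannot be settled from the documents. Under the stated assumptions the bias is at most about 1 point if known albuminuria is 0.8% or less of negatives, 1.4 to 2.4 points at 2%, and 3.2 to 5.3 points at 5%, against a planned 10. The conclusion is confined to the renal-testing endpoint. It justifies an inexpensive pre-specified analysis; whether eligibility itself should change is open to debate.

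**What to change.** 1. Reconcile sections 4.1, 4.2 and 8.3 with sections 1.1 and 1.2: state whether recorded albuminuria counts as measured CKD, and carry the answer into the EHR data run.
2. From the 12-month pre-randomization pull, flag any recorded ACR above 30 mg/g, or the PCR equivalent in the Table 1 note. Report the flag, and prior urine albumin testing, by APOL1 status.
3. Pre-specify the primary renal-testing contrast with flagged participants excluded, or with the flag as a covariate. Run the same analysis for SBP as supportive only.

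The cost is one line in the EHR query and a sentence or two in the SAP. Excluding flagged participants loses some precision, more among positives: if 5% of negatives are flagged, power for 40% versus 30% in that analysis is about 82% to 83% instead of 87%. At 2% it stays at 85% to 86%. Adjusting for the flag keeps the full sample. The flag finds only albuminuria recorded within the 12 months pulled.
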